3.1. Aim and Objective

The aim of the clinical investigation is to evaluate safety of Biatain Silicone, when used as prophylactic prevention on hospital-admitted patients at risk of developing a pressure injury.

- **Primary objective:** Evaluate safety

- **Exploratory objective:** Establish the proportion of subjects, that develop pressure injuries during hospitalization while wearing Biatain Silicone Sacral

[figure not shown]
The proportion of hospital-acquired pressure injuries will be compared to relevant existing proportions in literature³.

4. Investigational device and comparator(s)

The Biatain Silicone Sacral product is a sterile pouch-packed, single use polyurethane foam dressings with silicone adhesive intended for wound management and can be used as part of a prophylactic therapy to help prevent skin damage e.g., pressure injuries.

The Biatain Silicone Sacral and dressings are available in different shapes to fit the sacral area of the body. In this investigation it will primarily be the heart-shaped product, which will be used. However, if needed the diamond shaped, can be chosen.

**Biatain Silicone Sacral,
item no. 39001**

**Biatain Silicone Sacral,
item no. 39000**

Figure 1: Biatain Silicone Sacral dressings.

The two Biatain Silicone Sacral dressings consist of the same five layers:

- Polyurethane (PU) top film – a permeable barrier film of PU that is printed with dots
- Tissue layer – a tissue layer of cellulose fibres
- Super absorber layer – a cellulose fibre matrix with super absorbing particles
- Biatain foam pad – a PU foam with a thickness of 2.3 mm
- Silicone adhesive bi-layer – a silicone adhesive gel

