5.1. General

The Clinical investigation is an open-labelled, non-comparative, single-arm, prospective, multi-center observational investigation.

Subjects will be applied Biatain Silicone Sacral dressing in the sacral area at Baseline Visit / V1 in a test period up to 7 days or until discharged.

In total, 67 hospital-admitted patients will be enrolled. Each subject will have a screening visit (V0/Day 0), a Baseline visit (V1/Day1) and daily visits (V2/Day2 to V8/termination visit) performed. If the subject is discharged prior to visit 8, the termination visit will be performed at the day of the discharge.

All visits will be carried out by the Principal Investigator or delegate.

Before scheduling V0 the subject will be informed about the investigation, where the PI or delegate will give a detailed information about the requirements, the content and what it involves participating in the investigation. See section 6.4 for recruitment.

Screening visit (V0/Day0) and Baseline visit (V1/Day1) can be performed the same day. If the subject wishes to re-consider his or her participation after Screening (Visit0/Day0), the subject has the right to wait minimum 24 hours before decision to participate. If the subject hereafter decides to participate in the clinical investigation, Baseline visit (V1/Day1) will be scheduled, and the inclusion procedures will be performed. Screening visit/V0 and baseline visit must be performed on following days unless performed the same day.

[figure not shown]

Figure 2: Study Design CP346

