5.4. Exploratory endpoint

Hospital-acquired sacral pressure injuries during investigation period (Yes/No)

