5.9. Total expected duration of clinical investigation

The dates below are approximate, and no subjects will be enrolled before all required approvals have been obtained. If changes are required, applicable EC and regulatory authorities will be notified.

First subject enrolled: August 15th 2022.

Last subject enrolled: December 1st 2022.

Last subject completed: December 8th 2022.

Final report: June 2023.

6. Clinical Investigation population

The clinical investigation will be conducted with 67 hospitalized subjects enrolled at 3 clinical investigation sites. Each site will enrol about 22-24 subjects at a competitive rate, until the investigation target of 67 subjects is reached.

According to the sample size calculations (see section 10.2) 50 subjects are required to complete the investigation with at least 24 hours of wear time to be counted as completers. Considering a drop-out rate of 30%, the required total number of subjects to be enrolled in the trial shall be 67.

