10.1. Statistical design, method and analytical procedures

Definition of analysis populations

Safety populations and Intention to Treat (ITT) will be defined at a formal data review meeting before database lock. As a minimum, the data manager, the clinical manager and the statistician will be involved in the classification of subjects.

The safety population will be constituted by all subjects with valid informed consent. The ITT population (full analysis set) will be constituted by all subjects with valid informed consent, who have been exposed to the Test Product, with information on at least one endpoint.

The summary of the primary and secondary endpoints will be based upon the safety population, whereas the statistical analysis of the exploratory endpoint will be based on the ITT population. Invalid individual data points may be omitted from analysis even though the corresponding subject is part of the ITT population. Any exclusion of data points will be documented.

A formal per protocol (PP) population is not planned due to the explorative nature of the investigation. Considering the data obtained it might be considered to make additional explorative analyses based on a subset of the ITT population.

Analysis of the endpoints and baseline data.

The endpoints as well as baseline assessments will be listed and summarized by descriptive statistics. The summaries will be made for relevant visits (baseline or V1-V8), separately.

Summary statistics for continuous variables are presented with N, Mean, SD (standard deviation), Median, Min and Max, where N denotes the number of subjects contributing with non-missing data. For discrete variables, summary statistics are presented with N and percentage, where percentage is based on the total number of subjects/observations with non-missing data.

The incidence rate (proportion) of hospital-acquired pressure injuries in hospital-admitted patients will be estimated based on the exploratory endpoint (pressure injuries: Yes/No). The proportion of completed subjects answering "Yes" will be calculated. By use of an exact test in the Binomial distribution a 95% confidence interval will be estimated for the proportion.

All statistical analysis will be performed with SAS (version 9.4/Enterprise Guide version 7.1).

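### Section 10.1 assigns the pressure-injury endpoint to the ITT population but calculates its rate among completed subjects, a term it does not define

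*Combined protocol and SAP*

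**What the plan says.** Section 10.1 defines the ITT population as subjects with valid consent "who have been exposed to the Test Product, with information on at least one endpoint". It sets no completion or wear-time condition. The primary and secondary endpoints are summarised in the safety population, "whereas the statistical analysis of the exploratory endpoint will be based on the ITT population". Later in the same section the estimation sentence begins "The proportion of completed subjects answering" Yes, and the exact binomial interval is attached to that proportion.

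Section 10.1 does not say what makes a subject completed. Section 6 does give a criterion: "50 subjects are required to complete the investigation with at least 24 hours of wear time to be counted as completers". Section 6.5 treats more than 17 dropouts as meaning fewer than 50 completers, without defining a dropout. Section 10.2 bases its precision on 50 completing subjects out of 67 enrolled.

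The objective in section 3.1 has no completion condition: "Establish the proportion of subjects, that develop pressure injuries during hospitalization while wearing Biatain Silicone Sacral". Nor does the endpoint in section 5.4, which covers injuries during the investigation period. Section 7.1 places the injury Yes/No question at the termination visit, which may be Day 8, the day of discharge or an earlier termination date.

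**The concern.** Two statements in one section point to different sets for the same reported figure. If completed carries the section 6 meaning, an exposed subject who is not a completer, for example one who leaves before 24 hours of wear, belongs to the ITT population and can have an injury recorded at early termination. That injury would then be missing from both the rate and its interval.

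This is the only endpoint with a planned interval estimate. Section 10.2 relies on it for comparative conclusions, and section 10.4 requires it to be comparable with the published 5.3% [2.3%; 10.1%]. Few events are expected (section 10.2 assumes a true rate of 1.2%), so one subject counted or not counted visibly moves the upper limit. If the wording stays open, the choice could be made at the data review meeting before database lock, when the outcomes of this open, single-arm study can be seen.

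**Working it through.** **Inputs.** Enrolled 67 and completers at least 50 (sections 6 and 10.2). Two-sided 5% level (10.3). Exact binomial interval (10.1 and 10.2). The number of exposed and assessed non-completers is not in the documents. I take 3, 5, 10 and 17 as assumed values.

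**The plan's own figures.** 67 − 50 = 17, which agrees with the threshold in section 6.5 (17/67 = 25.4%). Taken literally, the 30% drop-out in section 10.2 gives 0.30 × 67 = 20.1, leaving about 47. So 17 is a planning figure, not a bound. The 7.2% target in section 10.2 is met at n = 50 only with no events, since 0/50 gives 7.11% and 1/50 gives 10.65%. The power attached to that target is a separate matter, and nothing below uses it.

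**Formulas (exact 95% upper limit U).**
- No events: U = 1 − 0.025^(1/n). For n = 50, 1 − 0.025^(1/50) = 7.11%.
- One event: U solves (1 − U)^n + n·U·(1 − U)^(n−1) = 0.025. For n = 50, U = 10.65%. For n = 53, U = 10.07%. For n = 67, U = 8.04%.

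**Results.** The completer set is 50 throughout. The ITT set is 50 plus the assumed number of exposed, assessed non-completers.

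| Assumed non-completers in ITT | ITT n | Upper limit, 0 events | Upper limit, 1 event |
|---|---|---|---|
| none (completers only) | 50 | 7.1% | 10.6% |
| 3 | 53 | 6.7% | 10.1% |
| 5 | 55 | 6.5% | 9.7% |
| 10 | 60 | 6.0% | 8.9% |
| 17 (extreme case) | 67 | 5.4% | 8.0% |

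**Three cases, completer rate against ITT rate.**
1. No injury: 7.1% against 6.7% to 5.4%.
2. One injury, in a completer: 10.6% against 10.1% to 8.0%. The point estimate is 1/50 = 2.0% against 1/53 = 1.9% to 1/67 = 1.5%.
3. One injury, outside the completers: 7.1% (0/50) against 10.1% (1/53) to 8.0% (1/67).

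Cases 1 and 2 make the ITT figure the more favourable one, and case 3 makes it the less favourable one. The direction is therefore not known in advance. That 1/53 gives 10.1%, the same as the upper limit of the published interval, is a coincidence. The plan uses neither 7.2% nor 10.1% as a decision limit.

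**The case against.** The best reply is that the two statements can be reconciled. Section 10.1 bases percentages for discrete variables on non-missing data, and the Yes/No item is answered once, at termination, including early termination. A completed subject could then simply be an ITT subject with an answered item, which leaves one denominator. This reading is possible, but the text does not state it. Sections 6, 6.5 and 10.2 use completers as a distinct group. If the loose meaning is intended, the same one-sentence change states it.

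The gap may also be small. Section 5.1 treats early discharge as planned conduct: "If the subject is discharged prior to visit 8, the termination visit will be performed at the day of the discharge". Inclusion needs an expected stay of more than 24 hours, and the record search in section 6.4 uses 72 hours. A reader might infer that every early-terminated subject is excluded. The documents do not support that, because a subject discharged early with at least 24 hours of wear may well count as a completer. Nor is 50 against 67 the expected contrast. Enrolment occurs at consent (section 6.6), which can precede application, and subjects lost before application are in neither set.

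A reader might also infer that the plan has no completer definition, or that an injury could vanish from the report. Section 6 supplies a criterion, and section 10.1 states that "The endpoints as well as baseline assessments will be listed and summarized by descriptive statistics", so the injury should still appear in the listing. Finally, the endpoint is exploratory. These points limit the consequence. They do not remove the mismatch.

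**Conclusion.** The point holds as a mismatch within section 10.1, confined to the injury rate and its exact interval. As written, the section supports two denominators. On the section 6 meaning of completer, the narrower one can leave out an injury that the trial has collected.

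Under the assumption of 50 completers and 3 to 17 exposed and assessed non-completers, the upper limit shifts by 0.4 to 1.7 percentage points with no injury (7.1 − 6.7 and 7.1 − 5.4). With one injury outside the completers it shifts by 3.0 to 0.9 points (10.1 − 7.1 and 8.0 − 7.1). These are illustrations, not bounds, and they say nothing about how likely such an injury is.

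It would go too far to say that the completer wording favours the device or overturns a conclusion. The shift can go either way, section 10.4 asks only for comparability, and no numerical limit decides the outcome. The textual mismatch is certain. Its effect on the reported rate cannot be determined from the documents. The change is worth making because it is cheap and the rate is the figure that the plan compares with the literature.

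**What to change.** In section 10.1 replace the completed-subjects sentence with wording such as: *the number of ITT subjects with a sacral pressure injury recorded at any post-application inspection or at termination (including early termination), divided by all ITT subjects with a non-missing termination Yes/No answer or an injury recorded at an earlier inspection, with exact 95% CI.*

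List ITT subjects without a termination answer, and do not count them as injury-free on the strength of an earlier clean inspection. The non-missing condition is needed because ITT membership requires information on only one endpoint, which may not be this one. Use the section 6 completer definition consistently in sections 6.5 and 10.1, say in section 6.5 what a dropout is, and report the completer proportion as a sensitivity analysis.

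The data should already exist. The termination item is in section 7.1, inspections and eCRF reporting are scheduled for visits 2 to 7 (section 7.2), and section 7.3 requires all observations to be recorded.

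The cost is one sentence, aligned definitions and one extra summary line. The ITT rate may be slightly more or less favourable than the completer rate. A subject without a termination answer enters the denominator only if an injury was recorded earlier, which leans the rate slightly upward. The listing shows how many subjects this concerns.

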10.2. Sample size

A sample size of 67 subjects will be enrolled with a minimum of 50 completers. This number is assessed to be sufficient to evaluate safety of the product.

The exploratory purpose of the investigation is to estimate the proportion of hospital-acquired pressure injuries in hospital-admitted patients with a 95% confidence interval. The confidence interval is then to be compared with the confidence interval of the results found by Mölnlycke. In the Mölnlycke investigation, the incidence in the control group was estimated to 5.3% [2.3%; 10.1%]³. 50 completing subjects will give a power of more than 80% to show an upper 95% confidence limit of 7.2% or less. This calculation assumes, that the true incidence rate for Biatain Silicone Sacral is 1.2% as we expect it to be as good as the intervention group in the Mölnlycke investigation³. It is further assumed that the confidence interval will be estimated as an exact confidence interval for binomial proportions. The precision of the estimated rate and the chosen sample size is evaluated to be sufficient to draw comparative conclusions between the rate of hospital-acquired sacral pressure injuries found in the suggested observational investigation and rates of hospital-acquired pressure injuries reported in literature.

To account for an estimated drop-out rate of 30%, 67 subjects must be enrolled to assure, that 50 subjects will complete the investigation.

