5.2. Primary endpoint

Number of Adverse Events

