10.4. Pass/fail criteria

There will be no formal success criteria for safety in this PMCF investigation.

The estimate rate (proportion) of hospital-acquired pressure injuries in hospital-admitted patients with a 95% confidence interval must be comparable to the confidence proportion and interval of the results found by Mölnlycke (5.3% [2.3%; 10.1%])³.

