18.1. Adverse events

An adverse event is any untoward medical occurrence, unintended disease or injury, or untoward clinical signs (including abnormal laboratory findings) in subjects, whether or not related to the investigational medical device(s) or the comparator(s), or the procedures involved. The adverse event shall be marked with the intensity mild, moderate or severe. This could include events such as headache or dizziness.

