18.2. Adverse device effect

An adverse event, which is related to the use of the investigational medical device, is an adverse device effect, and should be marked as unlikely related, possible related, probable related or with causal relationship on the adverse event form.

The definition of an adverse device effect includes any event resulting from insufficiencies or inadequacies in the instruction for use, deployment, implantation, installation and operation, or any malfunction of the medical device, as well as any event resulting from use error or from intentional misuse of the device.

Table 6 lists anticipated adverse device effects that may occur, based on the IFU and their likely incidence rates based on adverse events reported in clinical studies⁴.

Table 6

ANTICIPATED ADE	INCIDENCE RATES
Local pressure injury/Erythema*	1-10%
Skin irritation/inflammation/itching	0.1 %-1%
Maceration and/or local fungus infection of the skin	0.01-0.1%
Pain	0.01-0.1%
Blistering	0.01-0.1%
Allergic skin reaction	Not known

* *Temporary redness/erythema upon removal of the sacral bandage is not considered an adverse device effect, however an abnormal development in intensity or duration should be considered as such.*

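### Section 10.2 calls 67 enrolled and 50 completers enough to evaluate safety without any figure, and this is not credible for individual device effects at or below about 1%

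*Combined protocol and SAP*

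**What the plan says.** The primary objective in section 3.1 is to "evaluate safety". The primary endpoint in section 5.2 is "Number of Adverse Events", and section 18.1 counts events "whether or not related to the investigational medical device(s) or the comparator(s), or the procedures involved".

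On size, section 10.2 states "A sample size of 67 subjects will be enrolled with a minimum of 50 completers" and adds "This number is assessed to be sufficient to evaluate safety of the product". The power and precision text that follows in that section concerns the exploratory pressure-injury proportion. Section 10.4 says "There will be no formal success criteria for safety in this PMCF investigation".

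On analysis, section 10.1 says "The summary of the primary and secondary endpoints will be based upon the safety population". That population requires valid consent but not use of the dressing. The summaries are descriptive, with N and percentage for discrete variables. An exact 95% interval is planned only for the exploratory endpoint.

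Table 6 in section 18.2 lists six anticipated device effects with their likely incidence:

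- local pressure injury or erythema: 1-10%
- skin irritation, inflammation or itching: 0.1-1%
- "Maceration and/or local fungus infection of the skin": 0.01-0.1%
- pain: 0.01-0.1%
- blistering: 0.01-0.1%
- allergic skin reaction: not known

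Nothing in the plan links this table to the sample size.

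**The concern.** A claim that a sample is large enough to evaluate the safety of a product needs some statement of what the sample can detect or exclude. None is given, and with no safety criterion in section 10.4, nothing else in the plan defines sufficient.

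The plan's own rates suggest that most of the listed effects are too rare to be seen reliably in 50 to 67 people. For those effects a zero count would say little, and without an interval the report need not show how little. The all-cause count does not fill the gap: with no concurrent comparator, a total of adverse events in hospital patients cannot separate the dressing's effects from the course of illness.

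At stake is how a low count of device effects is read when the plan has declared in advance that the sample is adequate.

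**Working it through.** **The plan's own figure.** There is none to reproduce. Section 10.2 gives no safety calculation. Its power statement belongs to the exploratory endpoint and is not tested here.

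**Inputs.** n = 50 and n = 67 (section 10.2); the lower and upper ends of each Table 6 range (section 18.2); two-sided 5% level (section 10.3). Assumptions: the rates are per subject over the wear period, and all n subjects wear the dressing.

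**Chance of seeing an effect at least once:** 1 - (1 - p)^n.

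- p = 1%, n = 50: 1 - 0.99^50 = 1 - 0.605 = 39.5%
- p = 1%, n = 67: 1 - 0.99^67 = 1 - 0.510 = 49.0%

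The other entries follow in the same way:

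| Effect (Table 6 range) | n = 50 | n = 67 |
|---|---|---|
| Pressure injury/erythema (1-10%) | 39.5% to 99.5% | 49.0% to 99.9% |
| Skin irritation (0.1-1%) | 4.9% to 39.5% | 6.5% to 49.0% |
| Maceration, pain, blistering (0.01-0.1% each) | 0.5% to 4.9% | 0.7% to 6.5% |
| Allergic skin reaction (not known) | not calculable | not calculable |

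The chance reaches 50% at a true rate of 1 - 0.5^(1/n), which is 1.4% for n = 50 and 1.0% for n = 67. Hence the boundary of about 1%.

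**The four rarer effects together, assuming independence.**

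- Upper ends: p = 1 - 0.99 × 0.999^3 = 1.30%, giving 48% (n = 50) and 58% (n = 67).
- Lower ends: p = 1 - 0.999 × 0.9999^3 = 0.13%, giving 6% and 8%.

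**What zero events would exclude.** The exact two-sided 95% upper limit is 1 - 0.025^(1/n): 7.1% for n = 50 and 5.4% for n = 67. That is about 7 (5) times the top of the skin-irritation range, and 7.1/0.1 = 71 (5.4/0.1 = 54) times the top of the range for maceration, pain or blistering.

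**Scale of the limit.** A 95% chance of seeing one case requires a true rate of 1 - 0.05^(1/n): 5.8% for n = 50 and 4.4% for n = 67. Equivalently, n = ln(0.05)/ln(1 - p) gives 299 subjects at 1%, 2,995 at 0.1% and 29,956 at 0.01%.

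**Sensitivity to the denominator.** Table 6 does not say whether its rates are per subject or per dressing. Section 4.5 expects about one dressing per subject, so the two should be close. At the extreme of 7 dressings each (the supply allowance for the small size), with dressings independent, the exposures are 350 and 67 × 7 = 469. At 0.1% the chance is then 1 - 0.999^350 = 29.5% and 1 - 0.999^469 = 37.5%, so the three rarest effects would still probably be missed. At 1% it is 1 - 0.99^350 = 97.0% and 1 - 0.99^469 = 99.1%, so the finding for skin irritation at its upper rate does depend on the per-subject reading.

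**The case against.** The strongest reply is that the plan never defines evaluating safety as seeing each Table 6 effect. Its primary endpoint is a descriptive count of events from any cause, with no success threshold, in a post-market study of a CE-marked dressing. Small studies ordinarily cannot detect effects at 0.01-0.1%. This stands, and it rules out the tempting reading that Table 6 contradicts section 10.2. A statement without a figure cannot be contradicted by the rarity of some effects.

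Three other inferences also go too far:

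- *That the study would probably see no device effects.* Pressure injury or erythema would probably be seen over most of its range (92% at n = 50 if the rate is 5%). It also largely overlaps the exploratory endpoint, which already has a planned exact interval. Even the four rarer effects together reach 58% at their upper ends with n = 67. The finding holds effect by effect.
- *That the plan excludes per-subject percentages.* Section 10.1 promises N and percentage, over subjects or observations. Whether adverse events will be tabulated per subject is unclear rather than ruled out.
- *That a low count will be presented as proof of safety.* No passage says so, and section 20 requires the report to evaluate all the data critically.

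The reply does not supply a basis for the sentence. The claim in section 10.2 concerns the product, an all-cause total does not isolate the product, and skin irritation is one of only two risks that section 8.2 names. A descriptive analysis still needs a suitable denominator and a statement of precision.

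**Conclusion.** The sufficiency statement in section 10.2 is unsupported, and it is not credible for individual device effects at or below about 1%. Four of the five effects with a stated rate each have less than an even chance of appearing once, across their whole Table 6 range and at both sample sizes. The closest case is skin irritation at 1% with n = 67, which is nearly even.

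The result assumes per-subject rates over the wear period and full exposure. The source of the rates is a clinical evaluation report outside these documents, so the first assumption cannot be checked. On the second, consent may be signed at V0 while the dressing goes on at V1 (section 7.1), so some members of the safety population may never wear it. Taking 67 exposed subjects is therefore a best case, and a percentage over the whole safety population could be diluted.

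The documents do not show that the sample is wrong for a descriptive post-market study. They show that its limits are unstated and that the primary summary has no interval to reveal them.

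**What to change.** 1. In section 10.2, replace the sufficiency sentence with the precision delivered, for example: *Zero events of a given type among 50 (67) exposed subjects gives an exact two-sided 95% upper limit of 7.1% (5.4%); individual effects with incidence below about 1% are unlikely to be observed.*
2. In section 10.1, alongside the adverse event counts, report the number and proportion of dressing-exposed subjects with at least one adverse event and with at least one adverse device effect, each with an exact 95% confidence interval. Split the device effects by Table 6 category where the category is recorded; the adverse event form is not shown, so this should be confirmed.

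The cost is one sentence and one table. Section 7.2 already schedules review of adverse events and device effects from V1 to V8, and section 14 requires dates of use by subject, so exposure can be established. No extra patients are needed. The downside is a less favourable statement of what the sample can show.

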10.3. Level of significance and power

A two-sided significance level of 5% will be applied. For a description of the power see section 10.2 above.

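### With 50 completers, a true rate of 1.2% and an exact interval, the chance of an upper limit of 7.2% or less is 54.7%, not more than 80%

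*Combined protocol and SAP*

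**What the plan says.** Section 10.2 (Sample size) gives the only power statement in the plan: "50 completing subjects will give a power of more than 80% to show an upper 95% confidence limit of 7.2% or less". Two conditions follow. The assumed rate is that "the true incidence rate for Biatain Silicone Sacral is 1.2" per cent, taken from the intervention arm of the reference trial. The method is also fixed: "It is further assumed that the confidence interval will be estimated as an exact confidence interval for binomial proportions".

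Section 10.3 settles the sidedness and refers back: "A two-sided significance level of 5% will be applied. For a description of the power see section 10.2 above". Section 10.1 plans the same type of interval for the analysis, a 95% exact binomial interval on the yes/no pressure-injury endpoint.

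Other parts of the plan rely on this sentence. Section 6 attributes the requirement of 50 completers to the calculation in section 10.2. Section 10.2 goes on to judge the precision good enough for comparative conclusions against published rates. Section 10.4 requires the estimate and its interval to be comparable with the reference control group, 5.3% [2.3%; 10.1%].

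**The concern.** With 50 subjects and a rare event, the exact upper limit can take only a few widely spaced values. A limit of 7.2% lies just above the value for no events, so the target amounts to requiring none. An 80% chance of no events in 50 subjects is not plausible at a rate of 1.2%, which implies 50 × 0.012 = 0.6 expected events.

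If the figure is wrong, readers are misled about how often the study will deliver the precision it promises. A single pressure injury moves the upper limit past the reference control group's own upper limit of 10.1%. The comparison in section 10.4 would then be made with an interval that extends higher than the control interval.

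**Working it through.** **Inputs, all from the plan**

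- Completers: n = 50 (section 10.2)
- Assumed true rate: p = 0.012 (section 10.2)
- Target: upper 95% limit of 7.2% or less (section 10.2)
- Interval: exact binomial, i.e. Clopper-Pearson (sections 10.1 and 10.2)
- Level: two-sided 5%, so 2.5% in the upper tail (section 10.3)

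**Step 1: which event counts meet the target?** The exact upper limit U for x events solves P(X ≤ x | n, U) = 0.025.

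- x = 0: U = 1 − 0.025^(1/50) = 7.11%. This meets 7.2%.
- x = 1: (1 − U)^50 + 50·U·(1 − U)^49 = 0.025 gives U = 10.65%. This does not.
- x = 2: U = 13.71%. This does not.

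Only zero events pass. The margin is small: with 49 completers the zero-event limit is 1 − 0.025^(1/49) = 7.25%, and the target could not be met at all.

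**Step 2: the probability of meeting it.**

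- P(X = 0) = 0.988^50 = 0.5468
- P(X = 1) = 50 × 0.012 × 0.988^49 = 0.3321
- P(X ≤ 1) = 0.5468 + 0.3321 = 0.8789

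The power for an upper limit of 7.2% or less is therefore **54.7%**. The stated figure of more than 80% is not reproduced; the gap is at least 80 − 54.7 = 25.3 points. Allowing one event gives 87.9%, but that goes with a limit of 10.65%.

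**Step 3: other readings.**

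| Reading | Upper limit, 0 events | Upper limit, 1 event | Counts that pass | Power at 1.2% |
|---|---|---|---|---|
| n = 50, exact two-sided (as written) | 7.11% | 10.65% | 0 | 54.7% |
| n = 50, exact one-sided 95% | 5.82% | 9.14% | 0 | 54.7% |
| n = 50, mid-p two-sided | 5.82% | 9.47% | 0 | 54.7% |
| n = 50, Wilson two-sided | 7.13% | 10.50% | 0 | 54.7% |
| n = 50, Jeffreys two-sided | 4.88% | 8.97% | 0 | 54.7% |
| n = 50, Wald two-sided | 0% | 5.88% | 0 or 1 | 87.9% |
| n = 67, exact two-sided | 5.36% | 8.04% | 0 | 44.5% |
| n = 67, exact one-sided 95% | 4.37% | 6.89% | 0 or 1 | 80.8% |
| n = 67, mid-p two-sided | 4.37% | 7.14% | 0 or 1 | 80.8% |

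The three rows above 80% each contradict the text. The Wald interval is not exact. The other two use the enrolled number in place of the 50 completers, together with a one-sided or a non-exact limit.

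**Step 4: what would be needed for 80%.**

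- At n = 50 with only zero events allowed, the true rate would have to be at most 1 − 0.8^(1/50) = 0.445%.
- At 1.2% with the exact two-sided limit, one event first becomes allowable at n = 76 (power 76.8%). Two events become allowable at n = 98, the first n to reach 80% (power 88.6%).

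**The case against.** The arithmetic is hard to dispute, so the best defence is about consequence.

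- **Exploratory endpoint.** The primary endpoint is the number of adverse events, summarised descriptively. The plan has no formal success criterion for safety, and 7.2% is not a decision threshold anywhere. The exact interval planned in section 10.1 is valid whatever the power sentence says. This stands, and it limits the harm: no analysis result changes.
- **A separate rationale for the sample size.** Section 10.2 opens by judging 67 enrolled and at least 50 completers sufficient to evaluate safety, without using the 7.2% limit. This also stands. It does not support the numerical claim, and section 6 still attributes the 50 to the calculation in section 10.2.
- **An exact method can give just over 80%.** A one-sided exact limit at n = 67 does so (80.8%). That is a possible origin of the error, as is a Wald interval at n = 50; the plan does not show which. Neither matches the stated 50 completers, two-sided level and exact interval.
- **Other rates are not planning values.** Table 6 in section 18.2 lists "Local pressure injury/Erythema" at 1-10%. Across that range the chance of no events in 50 would be 0.99^50 = 60.5% at 1%, 0.95^50 = 7.7% at 5% and 0.90^50 = 0.5% at 10%. But Table 6 is an anticipated adverse-device-effect band that includes erythema, so these values are illustrative only and the finding does not rest on them.

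**Conclusion.** The power statement in section 10.2 is wrong on its own assumptions and should be corrected. The chance of an exact two-sided 95% upper limit of 7.2% or less with 50 completers is 54.7%. With more subjects up to the planned 67 it falls to 44.5%, because one event still does not pass. At the assumed 1.2%, at least one event occurs in 1 − 0.5468 = 45.3% of studies of 50, and the promised precision is then missed.

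The conclusion uses only the plan's n, rate, limit, interval method and level, and treats subjects as independent with a common rate, as the plan's binomial calculation does. It does not affect the primary safety summary or the validity of the planned interval. It does weaken the claim in section 10.2 that the precision supports comparative conclusions.

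**What to change.** Keep the sample size. In section 10.2, delete the claim of more than 80% power for the 7.2% limit and replace it with:

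> With 50 completers and a true incidence of 1.2%, the probability that the exact two-sided 95% upper limit is 7.2% or less (0 events) is 55%; the probability that it is 10.7% or less (at most 1 event) is 88%.

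It would also help to soften the later sentence in section 10.2 on comparative conclusions, since one event in 50 already gives a limit above the reference 10.1%.

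The cost is one sentence, or two with the optional change, and a less favourable stated figure; no extra patients are needed. The document is dated 28-03-2023, after the planned completion of the last subject on 8 December 2022 and before the planned June 2023 report. If the plan will not be amended again, state the correction in the clinical investigation report so that the figure of more than 80% is not carried forward.
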